## Outcome measures

HANA conditions will be defined as follows:

- a. Cardiovascular diseases
  - 1. Diagnosis of coronary heart disease, cerebrovascular disease, or peripheral artery disease by physician supported by relevant imaging results
  - 2. Subclinical atherosclerosis
    - i. Presence of plaques on carotid arteries
    - ii. cIMT greater than 75th percentile of population
- b. Diabetes and pre-DM
  - 1. DM will be defined by fasting glucose  $\geq 7.0$  mmol/L, or HbA1c  $\geq 6.5\%$ .
  - 2. Pre-DM will be defined by fasting glucose 5.6-6.9 mmol/L, or HbA1c 5.7-6.4%.
  - 3. Insulin resistance will be defined by HOMA-insulin resistance (fasting insulin ( $\mu$ U/ml)/22.5\*(glucose (mmol/l))  $>2.5$ ).
- c. Hypertension
  - 1. Systolic blood pressure  $\geq 130$  mmHg, or diastolic blood pressure  $\geq 80$  mmHg
- d. Metabolic syndrome
  - 1. Metabolic syndrome will be defined according to ethnic-specific criteria by the International Diabetes Federation, as any three of the following: (1) central obesity (waist circumference  $\geq 90$  cm in men and  $\geq 80$  cm in women); (2) triglycerides  $>1.7$  mmol/l; (3) reduced HDL cholesterol ( $<1.03$  mmol/l in men and  $<1.29$  mmol/l in women); (4) blood pressure  $\geq 130/85$  mm Hg; and (5) fasting plasma glucose  $\geq 5.6$  mmol/l; or receiving treatment for the above metabolic abnormalities.
- e. Obesity
  - 1. Overweight will be defined as BMI  $>23$  kg/m^2.

2. Obesity will be defined as BMI  $>26 \text{ kg/m}^2$ 

f. Fatty liver and liver fibrosis

1. Fatty liver will be expressed as CAP in dB/m, and hepatic steatosis grading will be defined as mild if CAP is 248-267 dB/m, moderate if 268-279 dB/m, and severe if  $\geq 280 \text{ dB/m}$ 
2. Liver stiffness will be expressed in kiloPascal (kPa). LS $>9.6-11.5\text{kPa}$  will be considered as advanced fibrosis, and LS $>11.5\text{kPa}$  as cirrhosis

g. Renal disease

1. Glomerular filtration rate (GFR) will be calculated using the 2009 CKD-EPI creatinine equation. Renal impairment will be defined as GFR  $<90 \text{ ml/min}$ , and albuminuria will be defined as urine albumin/Creatinine ratio  $\geq 30\text{mg/g}$ , according to KDIGO 2012 clinical practice guideline.
2. Kidney tubular dysfunction will be defined by:
  - i. Fractional tubular resorption of phosphate  $\{1- [(urine \text{ phosphate} \times \text{ serum Cr})/(urine Cr \times \text{ serum phosphate})]\} \times 100$  of  $<82\%$ ;
  - ii. Fractional excretion of uric acid  $\{[(urine \text{ uric acid} \times \text{ serum Cr})/(urine Cr \times \text{ serum uric acid})] \times 100\}$  of  $>15\%$ ;
  - iii.  $\beta 2\text{-microglobulin:creatinine} > 1000 \mu\text{g/g Cr}$ ; or
  - iv. RBP:creatinine  $>17\mu\text{g/mmol Cr}$

h. Osteopenia and osteoporosis

1. Osteoporosis is defined, according to World Health Organization criteria, as BMD T-score of  $\leq 2.5$  at the hip or spine in men  $\geq 50$  years old and post-menopausal women, or Z-score of  $\leq 2.0$  in men younger than 50 years old and pre-menopausal women.
2. Osteopenia is defined as a T-score between 1 and 2.49.

i. Chronic obstructive airway disease

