## **Data collection and investigations**

- a. Eligible subjects will attend Infectious Diseases clinic at the Prince of Wales Hospital for assessment.

The first study visit will be scheduled before or within four weeks of initiation of ART. Annual visits will be scheduled thereafter for 5 years. During each study visit, demographic and clinical data will be collected. Physical examination will be performed. Blood and urine tests will be done at fasting state. Imaging, including ultrasonography of carotid arteries, DEXA scan and fibroscan, will be performed. Stool samples will be collected for microbiota study.

- b. Clinical data

A structured standardized research tool will be used to collect demographic and clinical data:

1. Age, gender, smoking status, alcohol consumption, exercise
2. Co-morbid illnesses, including history or new diagnoses of hepatitis B and C, diabetes, dyslipidemia, hypertension, metabolic syndrome, and cardiovascular diseases, as well as all comorbidities included in the Charlson comorbidity score
3. Date of HIV diagnosis, latest CD4 counts, latest HIV viral load
4. Medication history, including anti-retroviral drugs and other medications

- c. Physical examination and anthropometric measurements

1. Body weight and height, and body mass index
2. Hip and waist circumferences
3. Blood pressure
4. For subjects aged  $\geq 50$  years old, assessment of frailty, including hand grip strength, balance tests, 6-metre walking speed, will be performed
5. Neurocognitive assessment
  - i. International HIV dementia scale  
<https://www.hiv.uw.edu/page/mental-health-screening/ihds>
  - ii. Montreal Cognitive Assessment
  - iii. Symbol digit modality test (SDMT)
  - iv. Action fluency: ask the patient to say as many things that people do in 1 minute
  - v. Cogstate platform neurocognitive tests
  - vi. DASS 21 for screening of mood
  - vii. Lawton Instrumental Activities of Daily Living
6. Quality of life assessment
  - i. EQ-5D-5L questionnaire
7. Lung function test
  - i. FEV1 and FVC will be performed in smokers.

- d. Blood tests:

The following blood tests will be performed after an 8-hour fast:

1. Glucose, insulin, HbA1c
2. Total cholesterol, LDL cholesterol, HDL cholesterol, triglyceride, apolipoprotein A and apolipoprotein E
3. Complete blood count, creatinine, urate, calcium, phosphate, urea, ferritin

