### Statistical analysis

a. The incidence rate of each HANA defined as above will be calculated as:

$$\text{incidence rate of HANA (per 100 person - years)} \\ = \frac{\text{number of new diagnosis of HANA at end of follow up}}{\text{number of persons at risk * number of years of follow up}} \times 100$$

b. The incidence rate of each HANA will be determined for subjects started INSTI-based regimens and other non-INSTI-anti-retroviral regimens.

c. Variables, including demographic, clinical, treatment-related, and laboratory parameters, will be evaluated for association with development of various HANA, in univariate and multivariate analyses. Analyses will be performed for the whole cohort, and subgroup analyses will be performed in those initiated INSTI-based regimens and other non-INSTI-based regimens.

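### Diabetes and hypertension are defined by measured values alone, so treated, controlled disease can be missed or coded as pre-diabetes and, unless recorded history sets the risk set, later counted as new

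*Combined protocol and SAP*

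**What the plan says.** Outcome measures item b.1 reads "DM will be defined by fasting glucose" of at least 7.0 mmol/L, or HbA1c of at least 6.5%. Item b.2 reads "Pre-DM will be defined by fasting glucose 5.6-6.9 mmol/L, or HbA1c 5.7-6.4"%. Item c takes a systolic reading of at least 130 "mmHg, or diastolic blood pressure" of at least 80 mmHg. None of these mentions an existing diagnosis or current treatment.

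Item d of the same list, metabolic syndrome, ends its criteria with "or receiving treatment for the above metabolic abnormalities".

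Statistical analysis item a begins "The incidence rate of each HANA defined as above will be calculated as". The numerator is the count of new diagnoses at the end of follow-up and the denominator is "number of persons at risk * number of years of follow up". Neither new nor at risk is defined. Item b reports the rates by regimen and item c relates development of each condition to covariates.

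Data collection and investigations, part b, records "Co-morbid illnesses, including history or new diagnoses of hepatitis B and C, diabetes, dyslipidemia, hypertension, metabolic syndrome, and cardiovascular diseases", and separately medication history, at each visit. No section says that these records decide who is a case or who is at risk. The exclusion criteria are pregnancy and refusal to consent only, so people with known, treated diabetes or hypertension can enrol.

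**The concern.** A rule based only on measured values cannot tell absence of disease from disease under control. Two errors follow.

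- **Missed cases.** Someone diagnosed and controlled between annual visits does not meet the definition at the next visit, and is never counted unless a later reading is high. This holds whoever is in the risk set.
- **Old cases counted as new.** If the same rule also sets baseline status, someone with known disease controlled at baseline is a baseline non-case, and becomes a new case at the first high reading. This holds only if the recorded history is not used to remove known cases.

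Incidence of each condition is the first objective and risk factors are the second. Even where the errors offset in a rate, people are on the wrong side of the outcome in the risk-factor models. For hypertension the regimen comparison is exposed as well. The Background says INSTIs improve pressure control in treated hypertension. If that holds here, fewer old cases read high and more new cases are already controlled on INSTI. Both effects lower the INSTI count, in the direction of the clinical hypothesis.

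**Working it through.** **1. Tracing people through the text.**

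| Person | Rule as written | With diagnosis or treatment counted |
|---|---|---|
| Treated diabetic, HbA1c 6.2%, fasting glucose below 7.0 mmol/L | pre-DM (6.2 lies in 5.7-6.4) | diabetes |
| Hypertension diagnosed in year 2, below 130/80 at every later visit | never a case | new case at the year-2 visit |
| Known hypertension, below 130/80 at baseline, high at year 3 | new case, unless history removes the person | baseline case, not at risk |

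**2. The plan's own figure.** The only precision statement is the 95% interval for a 20% risk with 400 people: 0.20 ± 1.96 × √(0.20 × 0.80/400) = 0.20 ± 0.039, or 16.1% to 23.9%. This agrees with the stated 16% to 24%. It concerns metabolic syndrome, which has a treatment clause, so it is unaffected.

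**3. Illustration of size.** The documents give no prevalence, treatment or control rates, so every input here is assumed. There are five annual visits and complete follow-up.

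- u: share treated and controlled at baseline
- h: share at or above threshold at baseline (cases under either rule, so removed)
- q: yearly chance of a high reading while treated
- i: true yearly incidence
- m: share of new cases already controlled at the next visit
- n = 1 − u − h: truly at risk

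False cases: F = u[1 − (1 − q)^5]. True cases: T = n[1 − (1 − i)^5]. True cases counted: C = n Σ i(1 − i)^(t−1)[1 − m(1 − q)^(5−t)], t = 1 to 5.

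If known cases stay in the risk set, the ratio of the rate as written to the correct rate is [(F + C)/(n + u)]/[T/n]. If history removes them, it is C/T.

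*Hypertension*, u = 0.05, q = 0.3, i = 0.075, m = 0.2, h = 0.30:

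- F = 0.05 × (1 − 0.168) = 0.0416, or 16.6 per 400.
- T = 0.65 × 0.3228 = 0.2098, or 83.9 per 400.
- C = 0.65 × (0.3228 − 0.2 × 0.1697) = 0.1878, or 75.1 per 400, so 8.8 are missed.
- Ratio = (91.7/280)/(83.9/260) = 1.02. C/T = 0.89.

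| h | False per 400 | Missed per 400 | Ratio | Old disease among counted cases |
|---|---|---|---|---|
| 0% | 17 | 13 | 0.98 | 13% |
| 20% | 17 | 10 | 1.00 | 16% |
| 30% | 17 | 9 | 1.02 | 18% |
| 40% | 17 | 7 | 1.04 | 21% |

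The 0% row is only for reference, since people already at or above 130/80 must leave the risk set. With q 0.2-0.4, i 0.05-0.10, m 0.1-0.3 and h 20%-40%, the ratio runs from 0.86 (h 20%, q 0.2, i 0.10, m 0.3) to 1.22 (h 40%, q 0.4, i 0.05, m 0.1). With known cases removed it is 0.80 to 0.96, whatever h is.

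*Diabetes*, u = 0.02, q = 0.3, i = 0.015, m = 0.2, h = 0: F = 0.02 × 0.832, or 6.7 per 400. T is 28.5 and C is 25.4 per 400, so 3.1 are missed. Ratio = (32.1/400)/(28.5/392) = 1.10, and C/T = 0.89. With i 0.01-0.02, and q and m as above, u = 1% gives 0.86 to 1.13. Setting h to 0 leaves in people already diabetic by measurement; removing them would raise the ratio slightly.

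*Regimen comparison, hypertension.* Assume equal i, u and h in both groups, a modest contrast of q = 0.25 (INSTI) against 0.35 (other), m = 0.2, i = 0.075 and h = 0.30. The counts per person are 0.0381 + 0.1853 = 0.2235 and 0.0442 + 0.1899 = 0.2341, a ratio of 0.95 where the truth is 1. With known cases removed it is 0.1853/0.1899 = 0.98.

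**The case against.** The best defence is the wording of the rate itself. It counts new diagnoses among persons at risk, and the visit form records history of diabetes and hypertension by name. The ordinary reading is that someone with a recorded history is neither at risk nor new. This stands as a real mitigation, and it makes the old-case error conditional. It does not reach the missed cases or the pre-DM coding, and no section ties the recorded history to the analysis.

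Second, glucose, HbA1c and pressure are measured every year, so a case first found at a study visit is counted. Only disease found and controlled outside the visits is lost, and the documents do not say how much that is. This also stands; it limits the size but not the mechanism.

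Third, uniform measurement is a defensible choice and most of the list uses it. Cardiovascular disease relies on "Diagnosis of coronary heart disease, cerebrovascular disease, or peripheral artery disease by physician supported by relevant imaging results", but no reading at a visit could replace that, so it does not show inconsistency. Metabolic syndrome does, because there treatment counts alongside measured values.

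A reader might infer more than the documents support:

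- *That known diabetics or hypertensives will be counted as new, or that the rates are inflated.* The plan does not say how baseline status is set, and the two errors oppose each other.
- *That the distortion is large.* A diabetes ratio of 1.49 needs four assumed inputs at their extremes together (u 3%, q 0.4, i 0.01, m 0.1).
- *That the INSTI comparison is biased by a known amount.* A ratio of 0.82 needs q of 0.2 against 0.4 and m of 0.3 against 0.1 together. The Background gives a direction, not a size. Physicians choose the regimen, so equal baseline prevalence is also only an assumption.

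**Conclusion.** The definitions are wrong as written. For diabetes and hypertension, the stated rule misses disease controlled between visits and can code a treated, controlled diabetic as pre-DM. Counting old disease as new is a further possibility, open only while the risk set is undefined.

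The net sign and size of the effect on the rates cannot be derived from the documents. On the assumed mid-range inputs, the rate as written is about 0.89 of the correct rate for either condition if history removes known cases. If it does not, the ratio is about 1.00 to 1.04 for hypertension (20% to 40% above threshold at baseline) and about 1.10 for diabetes. A ratio near 1 is not reassurance: in the same hypertension illustration, 16% to 21% of counted cases are old disease, and this carries into the risk-factor models. An effect on the hypertension comparison by regimen depends on the Background statement holding in this cohort.

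**What to change.** For analysis classification only:

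1. In Outcome measures b and c, count a case of diabetes or hypertension as any of: the stated threshold met, a recorded physician diagnosis, or current disease-specific medication.
2. In Statistical analysis a, state that persons at risk excludes baseline cases under this rule. Count new cases by the same rule, assigned to the annual visit at which they are first recorded, since the form lists no onset or drug start dates.
3. Code pre-DM only in people who are not diabetic under this rule.
4. Report the measured-values-only definition as a sensitivity analysis, overall and by regimen.

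The cost is two reworded definitions, the pre-DM coding, the risk-set and new-case wording, and one added analysis. The diagnosis and medication data are already collected at each visit. There are two downsides. Medications with other indications need a coding rule, and recorded diagnoses depend partly on clinical contact, whereas study measurements are uniform. The sensitivity analysis would show whether the second matters.

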## **A prospective longitudinal cohort study to determine the incidence of HIV-associated non-AIDS conditions in newly diagnosed HIV-infected individuals initiating integrase inhibitor-based and other anti-retroviral regimens**

### **Background**

Integrase strand transfer inhibitor (INSTI) based-therapy is currently the recommended antiretroviral regimen in most guidelines. Efficacy in terms of virological suppression of INSTI-based regimens was either superior or non-inferior to other comparators in clinical trials performed in both treatment naïve and experienced individuals. Moreover, unlike other classes of anti-retroviral agents, transmitted drug resistance was uncommon even after years of introduction of INSTI on a population level, potentially allowing this class of drug to remain as recommended first-line treatment in the future.

Previous clinical trials comparing INSTIs and other anti-retroviral regimens in treatment-naïve individuals consistently showed lower discontinuation rates secondary to adverse reactions. For treatment-experienced individuals, switching from non-nucleotide reverse transcriptase inhibitor (NNRTI) or protease inhibitor (PI)-containing to an INSTI-containing regimen often resulted in better lipid profiles as well as tolerability and patient satisfaction. INSTIs have been shown to improve blood pressure control in those with underlying hypertension receiving anti-hypertensive treatment. INSTI also had lesser decline in bone loss when compared to protease inhibitors. On the other hand, integrase inhibitors have been reported to be the cause of metabolic complications, and neuropsychiatric adverse reactions. Transient drop in renal function and other renal complications in individuals taking some INSTIs had also been reported.

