#### **b. Inclusion criteria:**

1. Confirmed HIV infection by HIV antibody or RNA test
2. Age  $\geq 18$  years old
3. Anti-retroviral treatment naïve, within 6 months of initiation of anti-retroviral drugs, or switching ART regimens within 24 months
4. Agree to initiate anti-retroviral therapy (ART) as determined by in-charge HIV physician

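### Renal impairment needs no persistent GFR fall, so the INSTI v non-INSTI renal contrast depends on how long a treatment-related drop lasts and when baseline was taken

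*Combined protocol and SAP*

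**What the plan says.** Outcome measures, item g: "Glomerular filtration rate (GFR) will be calculated using the 2009 CKD-EPI creatinine equation". Then "Renal impairment will be defined as GFR" below 90 ml/min. The item attributes its renal definitions to a guideline ("according to KDIGO 2012 clinical practice guideline") but states no repeat sample, duration or confirmation. By contrast, the Fibroscan item under Data collection does set a validity rule for liver stiffness.

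Statistical analysis, item a, divides new diagnoses counted at the close of follow-up by persons at risk times years. It does not say whether a low value at any visit makes a case or only status at the last visit. Item b gives the rate separately for INSTI and non-INSTI starters. The clinical hypothesis is a lower incidence on INSTI.

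Background reports a "Transient drop in renal function" with INSTIs, and adds that "other renal complications in individuals taking some INSTIs had also been reported". Neither the outcome nor the analysis section returns to this.

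Baseline timing is described in three ways:
- Study design: assessments are made before ART begins.
- Data collection and investigations, item a: "The first study visit will be scheduled before or within four weeks of initiation of ART".
- Inclusion criteria, item 3: besides treatment-naïve people, those "within 6 months of initiation of anti-retroviral drugs, or switching ART regimens within 24 months".

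After baseline, "Annual visits will be scheduled thereafter for 5 years".

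**The concern.** A threshold crossed once, on a creatinine-based estimate, is sensitive to ordinary within-person variation and to any temporary treatment effect on the estimate. The protocol itself names such an effect for one of the two groups it compares.

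Where that effect falls in time decides how it is counted. After a pre-ART baseline, a drop still present at an annual visit can make the participant an incident case. If the drop is already present when baseline is taken on ART, the same participant may be below 90 at entry and leave the at-risk set. Renal case status then reflects baseline timing, regimen and noise as well as kidney disease. A renal difference between regimens, or the lack of one, would be hard to interpret.

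**Working it through.** **The plan's own figure.** The only precision figure is for metabolic syndrome: 0.20 ± 1.96 × √(0.20 × 0.80/400) = 0.20 ± 0.039, or 16.1% to 23.9%. This matches the stated 16% to 24% but says nothing about the renal outcome, for which no figure is given.

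**Inputs.** From the protocol: threshold 90 ml/min, five annual post-baseline visits, baseline before or after ART start. Assumed, because the protocol gives none: the GFR distribution, the within-person SD, the yearly decline, and the size and duration of the drop.

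**Step 1. Density of people near the threshold.** Let GFR be normal with mean m and SD s. The share of those at or above 90 whom a drop d takes below it is [Φ((90−m+d)/s) − Φ((90−m)/s)] / [1 − Φ((90−m)/s)].
- d = 5, m = 110, s = 12: (0.1056 − 0.0478)/0.9522 = 6%.
- d = 5, m = 100, s = 12: (0.3385 − 0.2023)/0.7977 = 17%.
- Over m = 100–110 and s = 12–15, the range is 6–17% for d = 5 and 16–37% for d = 10.

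These shares apply only if the full drop is present when GFR is measured.

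**Step 2. Noise alone.** For a stable true GFR of 96 and within-person SD 6, one reading is below 90 with probability q = Φ(−1) = 0.159. At least one of five: 1 − (1 − 0.159)^5 = 58%. Two consecutive: 9%. Last visit only: 16%. This noise is common to both groups and is not evidence of regimen bias.

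**Step 3. Timing.** Simulation with mean 105, SD 15, within-person SD 5 and decline 1 ml/min per year. At risk means a baseline reading of 90 or more. Entries are the share of those at risk who become cases over five visits, not rates per 100 person-years.

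| Assumed drop and baseline | At risk | Any visit | Two consecutive | Last visit |
|---|---|---|---|---|
| No drop | 83% | 22% | 10% | 13% |
| 10, pre-ART baseline, gone before year 1 | 83% | 22% | 10% | 13% |
| 10, pre-ART baseline, year 1 only | 83% | 32% | 12% | 13% |
| 5, pre-ART baseline, lasting | 83% | 37% | 22% | 25% |
| 10, pre-ART baseline, lasting | 83% | 52% | 36% | 40% |
| 10, on-ART baseline, lasting | 62% | 37% | 19% | 24% |
| 10, on-ART baseline, at baseline only | 62% | 8% | 2% | 4% |

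With mean 100–110 and within-person SD 5–8, the any-visit figures are 16–41% with no drop, 42–70% with a lasting drop of 10 after a pre-ART baseline, and 5–25% when the drop is present only at an on-ART baseline.

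**Step 4. What confirmation does.** It removes most of a one-visit drop (12% v 10%, against 32% v 22% on a single value). It does not remove a lasting one. For a drop of 10, the gap goes from 30 points (52% v 22%) to 26 (36% v 10%), and the ratio rises from 2.4 to 3.7.

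**The case against.** A reader might infer that the definition biases the renal outcome against INSTI. The documents do not support that. The reported drop is called transient and has no stated size or duration. The first scheduled post-baseline measurement is a year later, so the drop may have resolved. Participants enrolled on ART may already carry it at baseline, which can push the comparison the other way. Background also mentions other renal complications with some INSTIs, so part of any excess could be real. Nothing is said about how comparator regimens affect creatinine. All of this stands, and the net direction is undetermined.

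A reader might also infer that one low value at any visit makes a permanent case. That is a reading of silence: the incidence formula could equally mean last-visit status. The ambiguity does not remove the problem, since a lasting drop of 10 still gives 40% v 13% on the last-visit reading.

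It is fair to add that two-visit confirmation alone is not a cure (Step 4). Albuminuria and the tubular criteria are defined separately, and multivariable analyses with treatment-related variables are planned, so renal conclusions need not rest on GFR alone. These limit the consequence. But neither qualifies the GFR criterion, and baseline timing is not named as a covariate.

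**Conclusion.** The concern holds as a distortion of undetermined direction. It runs towards more INSTI cases if the drop is still present at an annual visit that counts, after a pre-ART baseline. It runs towards fewer if the drop is present at an on-ART baseline and has then resolved. There is none if the drop resolves between a pre-ART baseline and year 1. If the drop is present at an on-ART baseline and lasts, the assumed model gives fewer cases than with a pre-ART baseline (37% v 52%) but still more than with no drop (22%).

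The any-visit span of 8% to 52% around 22% shows how much depends on facts the protocol does not give. It rests wholly on assumed GFR values and an assumed 10 ml/min drop, and is not a forecast. The text itself establishes three things: no persistence rule, an unstated visit-counting rule, and inconsistent baseline timing. For one outcome among many, this is a cheap and worthwhile improvement.

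**What to change.** 1. Keep the threshold. For the regimen contrast, count renal impairment when GFR is below 90 at two consecutive annual visits, and report the single-visit rate beside it.
2. State whether status at any visit or at the last visit counts in the single-visit rate.
3. Because confirmation leaves a lasting creatinine shift in place, also analyse GFR change from the first on-treatment value. Adjust for or stratify by baseline timing (pre-ART or on-ART).
4. Read these results alongside albuminuria and the tubular markers.
5. Reconcile baseline timing across Study design, Inclusion criteria item 3, and Data collection item a, and record for each participant whether baseline was taken on ART.

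The cost is SAP wording and one extra analysis on data already collected, with no new visits or assays. There are two downsides. Cases first seen at the last visit stay unconfirmed and appear only in the single-visit rate. For participants with a pre-ART baseline, the first on-treatment value is the year 1 visit, so that analysis cannot see first-year change; it should accompany the confirmed rate, not replace it.

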### **Study design**

This is a prospective, longitudinal, cohort study. 400 newly diagnosed HIV-infected individuals attending HIV clinics in Hong Kong will be recruited. Clinical assessment, and laboratory and imaging studies will be performed at baseline prior to initiation of anti-retroviral regimen, than annually thereafter for 5 years. Choice of anti-retroviral regimen will be decided by the in-charge HIV physician. Incidence of development of various HANA conditions will be determined for those initiated INSTI-based regimens and other anti-retroviral regimens. An electronic platform will be used to formulate risk prediction for various clinical outcomes, and serve as a clinical decision support tool.

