1. FEV1/FVC  $<0.7$

j. Frailty and sarcopenia in those aged 50 and above

1. Frailty is defined by Frailty phenotype measurement, according to Fried definition

k. Sarcopenia is defined as appendicular lean mass (kg)/height(m^2)  $< 2$  standard deviations below the mean for young healthy adults (cut-offs were  $< 7.26 \text{ kg/m}^2$  for men and  $< 5.45 \text{ kg/m}^2$  for women)

[figure not shown]
l. Retinal vasculopathy

1. Presence of HIV retinopathy, retinal vein occlusions and retinal artery occlusions

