### **Electronic platform**

- a. An electronic database will be established for systematic collection of all the above clinical and laboratory data, and clinical outcomes.
- b. The collected data will be used to generate risk assessment for multiple HANA conditions. Clinical management will be recommended according to risk assessment.
- c. A report summarizing the risk assessment and diagnosis of each HANA condition will be generated for each patient after each study visit. The report will be submitted to their HIV physicians for further clinical management.

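### The bone cut-offs are printed without minus signs, so osteopenia falls inside osteoporosis and, applied literally, almost nobody is at risk of osteoporosis

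*Combined protocol and SAP*

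**What the plan says.** Item h of the Outcome measures section defines two bone conditions.

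- **Osteoporosis.** The sentence begins "Osteoporosis is defined, according to World Health Organization criteria, as BMD T-score of" and continues with a cut-off of 2.5 or less at hip or spine for men aged 50 or over and post-menopausal women. For younger men and pre-menopausal women it uses a Z-score of 2.0 or less.
- **Osteopenia.** "Osteopenia is defined as a T-score between 1 and 2.49".

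All four numbers are positive, and no other section restates them with a sign. The wording does not supply a direction either. By contrast, the sarcopenia definition (item k of the same section) is explicit, placing its cut-off in "standard deviations below the mean for young healthy adults".

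The definitions are used in two places. The Statistical analysis section, item a, says: "The incidence rate of each HANA defined as above will be calculated as" new diagnoses over persons at risk times years of follow-up; item b asks for the rate by INSTI and non-INSTI regimen. The Electronic platform section, item c, says: "A report summarizing the risk assessment and diagnosis of each HANA condition will be generated for each patient after each study visit"; that report goes to the HIV physician.

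**The concern.** A T- or Z-score counts standard deviations from a reference mean, and low bone density gives a negative score. A rule of at or below +2.5 therefore includes a person at the reference mean, and most people above it. A band from +1 to +2.49 picks out bone that is denser than average.

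The two lines also conflict with each other. They are meant as separate grades of one condition, yet every T-score in the osteopenia band also satisfies the T-score rule for osteoporosis.

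Bone matters in this study. The Background cites less bone loss with INSTIs than with protease inhibitors and names osteopenia and osteoporosis among the HANA conditions, and hip and spine DEXA is planned at each visit. If the printed rule were applied, the persons-at-risk denominator for osteoporosis would nearly vanish and the regimen contrast with it.

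**Working it through.** **The plan's own figure.** The protocol gives no expected frequency for the bone outcomes. Its one reproducible precision figure is for metabolic syndrome: 0.20 ± 1.96 × √(0.20 × 0.80 / 400) = 0.20 ± 0.039, or 16.1% to 23.9%, which matches the stated 16% to 24%. It does not depend on the bone definitions.

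**Logic, with no distribution needed.** Take the T-score group.

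1. Signed scores, as printed: the band 1 to 2.49 is a subset of all scores ≤ 2.5. Everyone labelled osteopenic is also labelled osteoporotic.
2. Unsigned magnitudes, meaning SDs below the mean: osteopenia at 1 to 2.49 now makes sense. Osteoporosis at ≤ 2.5 would mean 2.5 SDs below the mean or fewer, which again takes in osteopenia and normal bone.

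No single sign convention makes both printed lines work.

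**Size if applied literally.** Inputs from the protocol are the four cut-offs and the cohort of 400. The score distribution is an assumption: normal, mean +0.5 to -1.5, SD 1, with one case at SD 1.3. For mean m and SD s:

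- share meeting the T rule = Φ((2.5 − m)/s)
- share meeting the Z rule = Φ((2.0 − m)/s)
- share in the osteopenia band = Φ((2.49 − m)/s) − Φ((1 − m)/s)
- number at risk = 400 × (1 − share), as if all 400 were judged by that one rule

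At m = 0, s = 1: Φ(2.5) = 0.9938, Φ(2.0) = 0.9772, and Φ(2.49) − Φ(1) = 0.152. The numbers at risk are 400 × 0.0062 = 2.5 and 400 × 0.0228 = 9.1.

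| Assumed mean, SD | T ≤ 2.5 | Z ≤ 2.0 | T 1 to 2.49 | At risk of 400 (T rule / Z rule) |
|---|---|---|---|---|
| +0.5, 1 | 97.7% | 93.3% | 28.5% | 9.1 / 26.7 |
| 0, 1 | 99.4% | 97.7% | 15.2% | 2.5 / 9.1 |
| -0.5, 1 | 99.9% | 99.4% | 6.5% | 0.5 / 2.5 |
| -1, 1 | 99.98% | 99.9% | 2.3% | 0.1 / 0.5 |
| -1.5, 1 | >99.9% | 99.98% | 0.6% | <0.1 / 0.1 |
| -1, 1.3 | 99.6% | 98.9% | 5.8% | 1.4 / 4.2 |

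**Same cut-offs with minus signs.**

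| Assumed mean, SD | T ≤ -2.5 | Z ≤ -2.0 | T -2.49 to -1 | At risk of 400 (T rule / Z rule) |
|---|---|---|---|---|
| 0, 1 | 0.6% | 2.3% | 15.2% | 397.5 / 390.9 |
| -1, 1 | 6.7% | 15.9% | 43.2% | 373.3 / 336.5 |

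The two T-score categories then no longer overlap, and a usable at-risk group remains.

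**The case against.** **The signs may have been lost when the PDF was read.** No negative number appears anywhere else in the text, so survival of a leading minus cannot be tested. This stands as a reason to check the source PDF first. Loss is still the less likely explanation: the signs are missing both from values set as mathematics (2.5 and 2.0) and from plain text (1 and 2.49), while the subtraction sign in the phosphate resorption formula just above survives.

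**The intended meaning can be recovered.** The definition names WHO criteria, and the two bands are adjacent, so a knowledgeable analyst would probably apply negative values. This is fair, and it makes a notation error the likeliest cause. But this is the only written definition, the analysis refers back to it, and it does not work under either reading.

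**The percentages do not estimate harm in this cohort.** Agreed. The documents give no score distribution, no split between those judged by T-score and by Z-score, and no allowance for the rule using either hip or spine. The figures show only what a literal reading would do.

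**Stronger readings.** A reader might infer that wrong diagnoses have already reached physicians or patients. The documents show neither how the platform codes bone status nor any erroneous report. A reader might also infer that incident osteopenia would simply record gains in bone. A person could enter the band from below 1 by gaining bone, but also from above 2.49 by losing it.

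**Conclusion.** The bone definitions are wrong as written. Two conclusions follow from the printed text and the ordinary meaning of the scores: the osteopenia band covers above-average density, and in the T-score group it is a subset of osteoporosis.

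The effect on the analysis is conditional. If the printed rule is applied literally, and scores are assumed normal with mean 0 and SD 1, about 99.4% (T rule) or 97.7% (Z rule) already have osteoporosis at entry. That leaves about 2 or 9 of 400 at risk, if all were judged by one rule. Over assumed means from +0.5 to -1.5 at SD 1, at least 97.7% and 93.3% meet the rules, so the conclusion does not hinge on the mean chosen. Osteoporosis incidence by regimen could not then be estimated.

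The documents do not support saying that the bone outcome is lost. The DEXA measurements are unaffected, so classification can be redone. The sample size rests on metabolic syndrome and does not change.

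**What to change.** 1. Check item h in the source PDF. If the minus signs are there, the protocol text needs no sign correction.
2. If they are absent, correct item h so that all four cut-offs denote SDs below the reference mean: osteoporosis at T ≤ -2.5 or Z ≤ -2.0, and osteopenia between -1 and -2.5. Word the osteopenia limits so that the categories neither overlap nor leave the small gap between 2.49 and 2.5. Reconcile the final wording, including which end-points are inclusive, with the WHO criteria the protocol cites.
3. Confirm that the analysis programs and the electronic platform use the corrected signs.
4. Reclassify from stored DEXA scores only if the literal rule proves to have been coded.

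The cost is a short protocol correction and a check of the coded rule. No new data are needed.
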